oHCM	Obstructive hypertrophic cardiomyopathy
PDCC	Protocol deviation classification committee
PGI-C	Patient Global Impression of Change scale
PK	Pharmacokinetics
PKS	Pharmacokinetics analysis set
PRO	Patient reported outcomes
PT	Preferred Term
pVO ₂	Peak oxygen uptake
QTcF	Fridericia corrected QT
RER	Respiratory exchange ratio
SAE	Serious Adverse Event
SAP	Statistical Analysis Plan
SAQ-7	Seattle Angina Questionnaire -7
SAS	Statistical Analysis System (SAS®)
SD	Standard deviation
SOC	System Organ Class
SRT	Septal Reduction Therapy
TEAE	Treatment-Emergent Adverse Event
TESAE	Treatment-Emergent Serious Adverse Event
TSS	Total Symptom Score
ULN	Upper Limit of Normal
VAS	Visual Analogue Scale
VAT	Ventilatory anaerobic threshold
WHO	World Health Organization

SAP VERSION HISTORY

Version and Date	Revision	Rationale
Final 1.0	Not applicable: original version	Not applicable
Version 2.0	Synopsis and Section 7.6: updated testing hierarchy and removed the statement related to determination of the testing order of the duration of SRT eligibility and total workload.	The testing hierarchy was simplified from parallel gate keeping method to a closed testing procedure to allow the testing of the secondary endpoints including SRT eligibility at Week 24 at two-sided alpha level of 0.05 once the primary endpoint reaches statistical significance at a specified sequential testing order.
	Section 2.2.3: corrected typo in exploratory endpoints: number of patients with new or worsening ST depression during exercise at Week 12 and 24 by removing time point Week 12 added 1 exploratory efficacy endpoint	CPET is only performed at Week 24.
	Section 2.2.4: updated the definition of the endpoint of incidence of LVEF <50% with signs and symptoms of heart failure (concomitant adverse event of heart failure or dyspnea) and/or increase in NT-proBNP from baseline	Update was made to provide greater specificity to the increase in NT-proBNP ($\geq 30\%$ increase) in relation to worsening HF.
	Section 5.5.4: modified FAS definition by removing condition of requiring at least one post baseline efficacy measurement	Update was made to address FDA comments to the SAP.
	Section 7.2: added statement that if model assumptions are substantially violated, rank based analysis will be performed as supportive analysis.	Updates were made to address FDA comments to the SAP.
	Section 7.5: added additional analyses by IND Sites status	Updates were made to add additional analyses to have consistent scope of by IND sites status analyses
	Section 7.8: Remove COVID-19 sensitivity analyses from the secondary endpoints	The impact of COVID-19 reported on the study has been minimal.

Version and Date	Revision	Rationale
	Section 7.7.1: updated the reasons of invalid CPET	To use the same statements provided by the CPET laboratory used in the data transfer specification
	Section 7.7.4: updated to include criteria of condition when rank-based analysis will be performed and clarified that, if performed, rank-based analysis will be supportive analysis for the primary endpoint	Updates were made to address FDA comments to the SAP and provide specific criteria for the rank-based analysis to be used.
	Section 7.8.1: update the number of imputed datasets from 50 to 100	Updates were made per FDA comments to the SAP
	Section 7.8.1: clarified imputing missing Week 12 NYHA. Added sensitivity analysis for proportion of responders at Week 12 and 24 after treating patients with missing data as non-responder. Added statement to impute intermittent missing data use adjacent visits results in determining patients' SRT eligibility.	Updates were made per FDA comments to the SAP; added clarification statements on imputing intermittent missing data except Week 12 and Week 24 in determining patient's SRT eligibility
	Editorial updates made where applicable	To correct editorial issues

1. INTRODUCTION

The purpose of this statistical analysis plan (SAP) is to provide a technical elaboration of the planned analyses and detailed data displays to be included in the Clinical Study Report (CSR) for CY 6031 study.

This SAP was developed in accordance with International Council for Harmonisation (ICH) E9 and ICH E9 (R1) guideline. All decisions regarding final analysis, as defined in this SAP document, will be made prior to the study database lock. Further study information can be found in the protocol.

2. STUDY OBJECTIVES AND ENDPOINTS

2.1. Study Objectives

2.1.1. Primary Objective

To evaluate the effect of CK-3773274 on exercise capacity in patients with symptomatic obstructive hypertrophic cardiomyopathy (oHCM).

2.1.2. Secondary Objective

The secondary objectives of the study are listed as follows:

- To evaluate the effect of CK-3773274 on patient health status
- To evaluate the effect of CK-3773274 on New York Heart Association (NYHA) Functional Classification
- To evaluate the effect of CK-3773274 on post-Valsalva left ventricular outflow tract gradients (LVOT-G)
- To evaluate the effect of CK-3773274 on exercise capacity
- To evaluate the effect of CK-3773274 on duration of eligibility for SRT

2.2. Study Endpoints

2.2.1. Primary Endpoints

The primary endpoint of the study is Change in peak oxygen uptake (pVO₂) by cardiopulmonary exercise testing (CPET) from baseline to Week 24.

2.2.2. Secondary Endpoints

- Change in Kansas City Cardiomyopathy Questionnaire – Clinical Summary Score (KCCQ-CSS) from baseline to Week 12 and Week 24
- Proportion of patients with ≥ 1 class improvement in NYHA Functional Class from baseline to Week 12 and Week 24
- Change in post-Valsalva LVOT-G from baseline to Week 12 and Week 24
- Proportion of patients with post-Valsalva LVOT-G < 30 mmHg at Week 12 and Week 24
- Total duration of SRT eligibility during the 24-Week treatment period in patients who were SRT eligible at baseline
- Change in total workload during CPET from baseline to Week 24

2.2.3. Exploratory Endpoints

- Compared with baseline, proportion of patients at Week 24 achieving either:
 - Change from baseline of ≥ 1.5 mL/kg/min in pVO₂ AND ≥ 1 class improvement in NYHA Functional Class

OR

– Change from baseline of ≥ 3.0 mL/kg/min in pVO₂ AND no worsening of NYHA Functional Class

- Proportion of patients with >3 mL/kg/min improvement in pVO₂ and ≥ 1 class improvement in NYHA Functional Class
- Proportion of patients with improvement of $\geq 5, 10, 15$ and 20 points in KCCQ-CSS and KCCQ- Total Symptom Score (TSS) at Weeks 12 and 24
- Proportion of patients with resting LVOT-G <30 mmHg, post-Valsalva LVOT-G <50 mmHg, and NYHA Functional Class I at Week 12 and Week 24
- Proportion of patients with resting LVOT-G <30 mmHg, post-Valsalva LVOT-G <50 mmHg, and ≥ 1 class improvement in NYHA Functional Class at Week 12 and Week 24
- Change from baseline to Week 24 in CPET parameters of:
 - Ventilatory efficiency (VE/VCO₂ slope)
 - Circulatory power (VO₂ \times systolic BP)
 - Ventilatory anaerobic threshold (VAT)
- Proportion of patients who remain SRT eligible at Week 24 in patients who were eligible for SRT at baseline. Proportion of patients who remain SRT eligible will also be evaluated at other scheduled visit weeks
- Time to first SRT ineligibility status in patients who were SRT eligible at baseline
- Change from baseline to Week 24 in individual responses to the EuroQol 5-dimension 5-level instrument (EQ-5D-5L)
- Change from baseline to Week 24 in total score and domain scores for the Seattle Angina Questionnaire -7 (SAQ-7)
- Change from baseline to Week 24 in echocardiographic measurements of cardiac structure and of systolic function including:
 - Left ventricular ejection fraction (LVEF)
 - Left ventricular global longitudinal strain (LV GLS)
 - Left ventricular end-systolic and end-diastolic volumes (LVESV and LVEDV)
 - Left atrial volume index
 - Left ventricular mass index
 - Maximal wall thickness
- Change from baseline values in n-terminal prohormone brain natriuretic peptide (NT-proBNP), high sensitivity cardiac troponin I (hs-cTnI) and other biomarkers through Week 24; proportional change (post randomization/baseline) will also be calculated and used in the analysis

- Change from baseline to Week 24 in patients enrolled in Cardiac magnetic resonance (CMR) substudy in CMR measurements of:
 - Left ventricular (LV) mass index
 - LVEF
 - Septal, free wall and maximal wall thickness
 - Left atrial volume index
 - LVESV
 - LVEDV
 - Extracellular volume proportion
 - Late gadolinium enhancement proportion
 - Mitral regurgitation severity
- Time to Maximal ST Segment Depression on CPET ECG
- Time to 1 mm ST depression below Baseline on CPET ECG
- Maximal ST segment depression on resting ECG in mm at Weeks 12 and 24
- Number of patients with new or worsening ST depression during exercise at Week 24
- Change from baseline values in all other summary KCCQ scores (Physical Limitation, Symptom Stability, Symptom Frequency, Symptom Burden, Total Symptom Score, Self-efficacy, Quality of Life, Social Limitation, Overall Summary Score) at Weeks 12 and 24.
- Proportion of patients with LVH with strain pattern (typical+ atypical) on Electrocardiogram (ECG) at Weeks 12 and 24
- Proportion of patients with all LVH (with or without strain) on ECG at Weeks 12 and 24

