7.9. Analysis of the Exploratory Efficacy Endpoints

Exploratory endpoints are specified in [Section 2.2.3](#). Other echocardiography parameters and CPET parameters not listed as secondary endpoints or in [Section 2.2.3](#) may also be analyzed as exploratory endpoints. All 10 summary scores will be derived for KCCQ. Change from baseline in each summary scores (except CSS) to Weeks 12 and 24 will be analyzed as exploratory endpoints. Patients with ≥ 5 , 10 and 20 points improvement in KCCQ summary scores at Weeks 12 and 24 will also be summarized and analyzed. Domain scores and summary score of SAQ-7 will be derived. Health state for EQ-5D-5L and index value using US value set will be calculated. Analysis of change from baseline in index score and VAS score of EQ-5D-5L be performed. Proportional change in Valsalva and resting LVOT-G will be derived and analyzed as exploratory endpoints.

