11. APPENDIX

11.1. Patient-reported Outcome Scoring Algorithm

11.1.1. KCCQ

There are 10 summary scores within the KCCQ, which are calculated as follows:

1. Physical Limitation

- Code responses to each of Questions 1a-f as follows:

Extremely limited = 1

Quite a bit limited = 2

Moderately limited = 3

Slightly limited = 4

Not at all limited = 5

Limited for other reasons or did not do = <missing value>

- If at least three of Questions 1a-f are not missing, then compute
Physical Limitation Score = $100 * [(\text{mean of Questions 1a-f actually answered}) - 1] / 4$
(see footnote at end of this appendix for explanation of meaning of “actually answered”)

2. Symptom Stability

- Code the response to Question 2 as follows:

Much worse = 1

Slightly worse = 2

Not changed = 3

Slightly better = 4

Much better = 5

I've had no symptoms over the last 2 weeks = 3

- If Question 2 is not missing, then compute
Symptom Stability Score = $100 * [(Question\ 2) - 1] / 4$

3. Symptom Frequency

- Code responses to Questions 3, 5, 7 and 9 as follows:

Question 3

Every morning = 1

3 or more times a week but not every day = 2

1-2 times a week = 3

Less than once a week = 4

Never over the past 2 weeks = 5

Questions 5 and 7

All of the time = 1

Several times a day = 2

At least once a day = 3

3 or more times a week but not every day = 4
1-2 times a week = 5
Less than once a week = 6
Never over the past 2 weeks = 7

Question 9

Every night = 1
3 or more times a week but not every day = 2
1-2 times a week = 3
Less than once a week = 4
Never over the past 2 weeks = 5

- If at least two of Questions 3, 5, 7 and 9 are not missing, then compute:

$$S3 = [(Question\ 3) - 1]/4$$

$$S5 = [(Question\ 5) - 1]/6$$

$$S7 = [(Question\ 7) - 1]/6$$

$$S9 = [(Question\ 9) - 1]/4$$

$$\text{Symptom Frequency Score} = 100 * (\text{mean of } S3, S5, S7 \text{ and } S9)$$

4. Symptom Burden

- Code responses to each of Questions 4, 6 and 8 as follows:

Extremely bothersome = 1

Quite a bit bothersome = 2

Moderately bothersome = 3

Slightly bothersome = 4

Not at all bothersome = 5

I've had no swelling/fatigue/shortness of breath = 5

- If at least one of Questions 4, 6 and 8 is not missing, then compute

$$\text{Symptom Burden Score} = 100 * [(\text{mean of Questions 4, 6 and 8 actually answered}) - 1]/4$$

5. Total Symptom Score

= mean of the following available summary scores:

Symptom Frequency Score

Symptom Burden Score

6. Self-efficacy

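### KCCQ Symptom Stability already records change, so the points-improvement responder analysis that SAP 7.9 appears to apply to it misclassifies patients, and its within-arm change from baseline cannot be interpreted

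*SAP*

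**What the plan says.** SAP 11.1.1 derives Symptom Stability from Question 2 alone. The five ordered answers run from much worse (1) through not changed (3) to much better (5). A sixth option is coded to the middle: "I've had no symptoms over the last 2 weeks = 3". The score is 100 × (code − 1)/4.

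SAP 2.2.3 names this score for change from baseline at Weeks 12 and 24: "Change from baseline values in all other summary KCCQ scores (Physical Limitation, Symptom Stability". SAP 7.9 repeats the intention in general terms. It first states "All 10 summary scores will be derived for KCCQ", then "Change from baseline in each summary scores (except CSS) to Weeks 12 and 24 will be analyzed as exploratory endpoints", and then adds responders: "Patients with ≥ 5 , 10 and 20 points improvement in KCCQ summary scores at Weeks 12 and 24". It makes no exception for Symptom Stability.

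The responder endpoint in SAP 2.2.3 is narrower. It uses thresholds of 5, 10, 15 and 20 points, and only "in KCCQ-CSS and KCCQ- Total Symptom Score (TSS) at Weeks 12 and 24". The two sections therefore differ in both scope and thresholds.

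Under SAP 5.6 and 5.7.4, baseline for the KCCQ is Day 1 and change is the later value minus baseline. Under SAP 7.9.1, repeated continuous endpoints use the same MMRM as the secondary endpoints, and responders use a stratified CMH test. SAP 7.1 gives exploratory endpoints a nominal 0.05 with no multiplicity adjustment.

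**The concern.** The other KCCQ scores measure a level: how limited, how frequent, how bothersome. Subtracting Day 1 from Week 24 gives the improvement. The Symptom Stability answers already describe a movement, and 50 means either steady or free of symptoms. Subtracting one movement from another does not measure improvement, and a points threshold on the result does not identify patients who improved.

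At stake is how a set of exploratory rows will be read. Symptom Stability responder rows would stand beside those for Symptom Frequency and Symptom Burden, with nominal p-values, and would look comparable. Some patients counted as improvers would have reported no improvement, and some who reported being free of symptoms would be counted as unchanged or worse.

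**Working it through.** The plan states no figure for this score, so there is nothing to reproduce. The check applies its own scoring rule.

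**Step 1: possible scores.** From 100 × (code − 1)/4:

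| Answer | Code | Score |
|---|---|---|
| Much worse | 1 | 0 |
| Slightly worse | 2 | 25 |
| Not changed | 3 | 50 |
| Slightly better | 4 | 75 |
| Much better | 5 | 100 |
| No symptoms | 3 | 50 |

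**Step 2: change, later score minus Day 1 score.** MW, SW, NC, SB, MB and NS stand for the answers in the order above.

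| Day 1 ↓ / later → | MW | SW | NC | SB | MB | NS |
|---|---|---|---|---|---|---|
| MW | 0 | +25 | +50 | +75 | +100 | +50 |
| SW | −25 | 0 | +25 | +50 | +75 | +25 |
| NC | −50 | −25 | 0 | +25 | +50 | 0 |
| SB | −75 | −50 | −25 | 0 | +25 | −25 |
| MB | −100 | −75 | −50 | −25 | 0 | −50 |
| NS | −50 | −25 | 0 | +25 | +50 | 0 |

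**Step 3: thresholds.** The smallest positive change is 25. Thresholds of 5, 10 and 20 (and 15) therefore all select the patients with +25 or more. The planned responder analyses on this score are one analysis repeated.

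**Step 4: classification.**
- Not changed, then no symptoms: 50 − 50 = 0, a non-improver, the same as a patient who stayed at not changed.
- Slightly better, then no symptoms: 50 − 75 = −25, an apparent worsening.
- Slightly worse, then not changed: 50 − 25 = +25, an improver at every threshold.
- Much worse, then slightly worse: 25 − 0 = +25, also an improver at every threshold, although the later answer still reports worsening.

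**Step 5: within-arm change.** Suppose every patient in an arm scores 50 at Week 24. The mean change is then 50 minus the Day 1 mean, and the improver proportion is the share who answered much or slightly worse on Day 1. Both are fixed by the Day 1 answers, whether the 50s at Week 24 mean steady symptoms or none.

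**Step 6: between-arm contrast.** Let Y be the score at visit v, B the Day 1 score and T the treatment. The MMRM in SAP 7.8.1 and the code in 11.5 include baseline and baseline by visit, so for change:

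Y − B = α(v) + β(v)·B + τ(v)·T + strata + error.

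Moving B to the right:

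Y = α(v) + [β(v) + 1]·B + τ(v)·T + strata + error.

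Because β(v) is free at every visit, this is the same model with the baseline slopes relabelled. The treatment difference τ(v), its standard error and its p-value are identical for change and for level.

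**The case against.** The strongest reply is that 7.9 may be loosely worded. It opens by referring to 2.2.3 for the exploratory endpoints, and 2.2.3 confines responders to CSS and TSS. On that reading Symptom Stability has no responder analysis. This is a fair reading, and it is why 2.2.3 should not be cited as planning one. But the sentence in 7.9 follows directly on the derivation of all ten scores, speaks of summary scores generally and uses a different threshold list. A programmer following it as written would produce the rows.

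Two limits also stand. The full wording of Question 2 is not in the documents, so its meaning is read from its answer options. And the tie at 50 affects only patients who choose the no-symptoms option; someone whose symptoms cleared recently might answer much better and score 100.

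A reader might go further. Scheduled escalation ends at Week 6, so a sustained benefit could leave treated patients answering not changed or no symptoms at Weeks 12 and 24, and the change-from-baseline analysis might then seem to manufacture a false null. The documents do not support that causal claim. By Step 6 the treatment contrast is the same with or without subtracting baseline, so a near-zero difference would come from what the item asks and how it is coded. For the same reason, replacing change with mean level would not alter that contrast.

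**Conclusion.** The point holds as a minor one. Read as written, 7.9 defines a responder analysis on Symptom Stability whose three thresholds coincide and whose categories do not correspond to improvement. The within-arm change estimates planned in 2.2.3 and 7.9 have no clear meaning for this score. The between-arm MMRM contrast is not distorted by the subtraction.

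The reach is narrow: one of the nine KCCQ scores other than CSS (10 − 1), exploratory and at nominal alpha. It would be wrong to infer any effect on the KCCQ-CSS tests: under 11.1.1 Symptom Stability does not enter the Total Symptom, Clinical Summary or Overall Summary scores. The primary endpoint and the testing hierarchy are unaffected.

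The scoring results follow from 11.1.1 without any assumed answer distribution. How many patients would be misclassified depends on the Day 1 and later answers, which the documents do not give. The conclusion about responders assumes that 7.9 is applied literally.

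**What to change.** - **SAP 7.9, responders:** exclude Symptom Stability from the points-improvement analyses, and align their scope and thresholds with 2.2.3, that is CSS and TSS at 5, 10, 15 and 20 points.
- **SAP 2.2.3 and 7.9, change from baseline:** take Symptom Stability out. Instead tabulate its observed response categories by arm and visit, with no symptoms shown separately from not changed. The separate category carries the information that the common code of 3 removes.
- **Leave as they are:** the scoring in 11.1.1 and the change-from-baseline analyses of the other KCCQ scores.

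The cost is a short edit to two SAP sections and a replaced table. It needs no new data and no change to sample size or alpha. It does require that the raw answer to Question 2 is kept in the database as well as the code, since the code alone cannot separate the two answers. If the SAP can no longer be revised, SAP 5.4 allows a change to planned analysis to be documented in the clinical study report.

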2.2.4. Safety Endpoints

- Incidence of reported major adverse cardiac events (cardiovascular [CV] death, cardiac arrest, non-fatal stroke, non-fatal myocardial infarction, CV hospitalization)
- Incidence of new onset persistent atrial fibrillation
- Incidence of appropriate implantable cardiac defibrillator (ICD) discharges and aborted sudden cardiac death
- Incidence of LVEF <50% with at least one of the following:
 - Signs and symptoms of heart failure (concomitant adverse event of heart failure or dyspnea)AND/OR
 - Increase in NT-proBNP ($\geq 30\%$ increase), relative to results from the most recent previous visit and above the upper limit of normal, at the time of LVEF assessment <50%

Note signs and symptoms refer to AEs with onset date within ± 7 days relative to the date when LVEF $<50\%$.

- Incidence of LVEF $<40\%$
- Incidence of LVEF $<50\%$

Incidence of LVEF below 40% and 50% will be summarized for site read, core lab read and both.

- Incidence of treatment emergent adverse events (TEAEs)

2.2.5. PK Parameters

- $C_{\text{post dose}}$ and $C_{\text{pre-dose}}$

3. STUDY DESIGN

3.1. Summary of Study Design

This is a Phase 3, randomized, placebo-controlled, double-blind, multi-center trial in patients with symptomatic oHCM. Approximately 270 eligible patients will be randomized in a 1:1 ratio to receive CK-3773274 or placebo. Randomization will be stratified by use of beta-blockers (yes or no) and CPET exercise modality (treadmill or bicycle) and implemented in the Interactive Web Response System (IWRS). A cap on the number of patients taking beta-blockers and will not exceed approximately 70% of total enrollment. The number of patients taking disopyramide will be capped at approximately 10% of total enrollment. The number of patients with persistent atrial fibrillation at screening will also be capped at approximately 15%, and the number of patients using the bicycle CPET exercise modality will be capped at approximately 50% as well.

Investigational product (IP) will be administered orally once daily with or without food. During the initial six weeks of the treatment period, IP doses will be individually titrated at Weeks 2, 4, and 6 using echocardiography. Dose escalation at Weeks 2, 4, and 6 will occur only if a patient has a post-Valsalva LVOT-G ≥ 30 mmHg and a biplane LVEF $\geq 55\%$. Echocardiograms will be performed at each subsequent visit during the trial and the dose down titrated if necessary. The primary endpoint of pVO₂ will be measured by CPET at screening and at end of treatment (Week 24). If applicable, patients will continue taking background HCM medications consistent with regional clinical practice guidelines during the trial.

3.2. Definition of Study Drugs

Table 1 describes any study drug: IP (ie, aficamten) or placebo intended to be administered to a trial patient according to the protocol.

Table 1: Investigational Products

	Active	Placebo
IP/Product Name	CK-3773274	Placebo
Type	Drug	Drug
Dose Formulation	Tablet	Tablet
Unit Dose Strength(s)	5 mg	Matching placebo
Dosage Level(s)	5mg, 10mg, 15mg, 20 mg	
Route of Administration	Oral	Oral
Use	Experimental	Placebo
IMP and NIMP	IMP	IMP
Packaging and Labeling	IP will be provided in blister packs which will be labeled as required per country requirement	IP will be provided in blister packs which will be labeled as required per country requirement

